In this study we are recruiting women who have had preeclampsia in the past 5 years. We use the blood vessels in the skin as a representative vascular bed. Using a minimally invasive technique (intradermal microdialysis for the local delivery of pharmaceutical agents) we examine the blood vessels in a nuckle-sized area of the skin in women who have had preeclampsia. We make these measurements after the subjects take a placebo and after they take losartan (an angiotensin II receptor blocker) to test whether this treatment improves vascular function in these women. Because losartan can have dangerous effects on a fetus, women enrolled in this study will be required to use an effective form of birth control [hormonal patch, implant or pill; intrauterine device; consistent use of barrier contraceptive; or prior medical procedure to prevent pregnancy (i.e. tubal ligation or vasectomy in current partner)]. As a compliment to these measurements, we also draw blood from the subjects and isolate the inflammatory cells to test how sensitive their inflammatory responses are following the placebo and the losartan treatment.

A modification was submitted changing the eligibility requirements from having preeclampsia within the past 2 years, to within the past 5 years. This modification was made to help with recruitment for the study. Women who are breastfeeding are excluded from this study. Since many women are breastfeeding during those first 2 years after delivery, it reduced those that were eligible for the study. We changed it to delivering within the past 5 years to match the other preeclampsia studies in our lab (IRB #202203433, 202303202, 202303799).

I.5

Specify your research question(s), study aims or hypotheses (do not indicate "see protocol")

AIM: To determine the effect of systemic AT1R inhibition (oral losartan) on in vivo and in vitro measures of inflammation and endothelial function in women who have had preeclampsia (PE) . Utilizing a chronic (6 week) losartan intervention coupled with intradermal microdialysis and assessment of the inflammatory response to ang II stimulation in peripheral blood mononuclear cells (PBMC), we will test the hypotheses that therapeutic doses of the AT1R inhibitor augment endothelium-dependent dilation and reduce inflammation in PE.

HYPOTHESES

- 1: Chronic oral losartan therapy will augment endothelium-dependent dilation in PE by increasing nitric oxide-dependent dilation.

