The -80C freezer in 111 PSRB is a shared wet lab space. The door to this lab space is kept locked but those with keys to the shared lab space would be able to enter the room. Individuals with key access to 111 PSRB include:

[name]
[name], BS
[name], BA

X.7***Does your study meet the NIH criteria for a [Certificate of Confidentiality](#) or will you be applying for Certificate of Confidentiality?***

Yes

X.8***If yes, provide rationale:***

Per Section 2012 of the 21st Century Cures Act as implemented in the 2017 NIH Certificates of Confidentiality Policy, all ongoing or new research funded by NIH as of December 13, 2016 that is collecting or using identifiable, sensitive information is automatically issued a CoC.

XI. Data Analysis**XI.1*****Describe the analysis methods you will use, including, if applicable, the variables you will analyze***

The primary outcome variable will be cutaneous vascular conductance, which is calculated from laser-Doppler flux/mean arterial pressure. Three-way repeated measures ANOVA (treatment, MD site, dose) will be used to examine systemic treatment differences (losartan vs. placebo) and local

microdialysis treatment differences across the doses of pharmacological stimuli. Appropriate post-hoc analyses with corrections for multiple comparisons will be performed when main effects are identified, including potential confounding variables as covariates. Paired t-tests will be used to examine systemic treatment differences on pulse wave velocity.

XI.2***Provide the rationale or power analysis to support the number of subjects proposed to complete this study.***

Based on previous data examining chronic pharmacological intervention strategies we calculate that 10 subjects will be necessary to detect an effect size of 15% between microdialysis sites (1 sample RMANOVA, power=0.08, $\alpha=0.05$). Based on the duration of the intervention and prior experience, we anticipate that ~5 subjects will screen but not be eligible and of those that enroll, ~5 will drop out of the intervention, therefore, we suggest a total sample of 20 subjects.

XII. Future Research**XII.1*****Do you wish to keep any information about subjects involved with this research project so that members of the current research team may contact them in the future for your own research projects?***

Yes

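### The only power statement prints 0.08 and sizes the trial on a contrast between skin sites, so power for losartan versus placebo is not established

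*Combined protocol and SAP*

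**What the plan says.** Section XI.2 gives the only planning calculation: "10 subjects will be necessary to detect an effect size of 15% between microdialysis sites (1 sample RMANOVA, power=0.08", with alpha 0.05. It gives no SD, no within-woman correlation and no sidedness, and does not say whether the 15% is absolute, relative or standardised. About 5 screen failures and about 5 dropouts are added to reach 20, the number also entered in VI.1.

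The trial's question is stated in I.5: "AIM: To determine the effect of systemic AT1R inhibition (oral losartan) on in vivo and in vitro measures of inflammation and endothelial function". Hypothesis 1 reads "Chronic oral losartan therapy will augment endothelium-dependent dilation in PE by increasing nitric oxide-dependent dilation". Hypothesis 2 concerns angiotensin II sensitivity under losartan, and Hypothesis 3 concerns cytokines and the response of blood mononuclear cells.

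Under XI.1, "The primary outcome variable will be cutaneous vascular conductance", analysed by a repeated-measures ANOVA with treatment, site and dose as factors. That section separates the systemic comparison (losartan against placebo) from the local comparison between microdialysis perfusates. VII.E.6 defines the sites: acetylcholine without L-NAME, acetylcholine with L-NAME, angiotensin II, and norepinephrine, all at the same visit. The two treatments are given in a crossover (VII.D.29).

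**The concern.** The first fault is the printed power. Nobody sizes a study for an 8% chance of success, so the figure cannot be the intended one, and without an SD the reader cannot confirm what was.

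The second fault survives correction of the first. A difference between sites within a visit shows, for example, that L-NAME blunts the acetylcholine response. It does not show that losartan changes anything. Hypothesis 1 needs the change in the site difference between losartan and placebo, a difference of differences. Hypothesis 2 needs losartan against placebo at the angiotensin II probe. Hypothesis 3 uses no microdialysis site.

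The 10 completers, and hence the 20 women consented, rest on this one sentence. If losartan shows no effect, a reader who takes XI.2 with its decimal corrected could treat the result as an adequately powered negative when the power quoted belongs to a different comparison.

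**Working it through.** **Inputs from the documents.** n = 10 completers, alpha 0.05, effect 15%, power 0.08 (XI.2). Washout of at least 14 days, then 6 weeks on the second treatment (VII.E.6), so the two experimental visits are at least 2 + 6 = 8 weeks apart.

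**Assumptions.** Two-sided test; 15% read as 15 points; each contrast reduced to a single paired t-test. SDs are back-calculated because none is given.

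**Accrual.** 10 + 5 + 5 = 20. This reproduces.

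**Can n = 10 be reproduced?** Not from the documents, since the SD is missing. What can be found is the SD that n = 10 implies. With d = effect / SD of the paired difference, power is the probability that a noncentral t with 9 degrees of freedom and noncentrality d√10 exceeds 2.262 in absolute value.

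| Power | d | Implied SD of the difference = 15/d |
|---|---|---|
| 0.08 (as printed) | 0.179 | 83.9 points |
| 0.80 (assumed intended) | 0.996 | 15.1 points |

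With an SD of 10 to 30 points, only 2 or 3 women would be needed for 8% power, so 0.08 and n = 10 do not fit together at such SDs. At 0.80, n = 10 fits an SD of about 15. One-sided, 0.80 gives d = 0.853 and an SD of 17.6.

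**Treatment-by-site contrast (Hypothesis 1).** Take 0.80 as intended and suppose losartan-minus-placebo at each site has the same 15.1-point SD. If those two differences correlate ρ, the SD of the difference of differences is 15.1 × √(2(1 − ρ)). The effect detectable with 80% power is 15 × √(2(1 − ρ)).

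| ρ | SD | Power for 15 points, n = 10 | Detectable at 80% |
|---|---|---|---|
| 0 | 21.3 | 51% | 21 points |
| 0.25 | 18.4 | 63% | 18 points |
| 0.5 | 15.1 | 80% | 15 points |
| 0.6 | 13.5 | 88% | 13 points |
| 0.75 | 10.6 | 98% | 11 points |

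At ρ = 0, 18 completers would be needed for 80%.

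**Losartan versus placebo at one site.** Let the SD of the between-visit difference be k times the 15.1-point SD of the between-site difference.

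| k | SD | Power for 15 points, n = 10 |
|---|---|---|
| 0.75 | 11.3 | 96% |
| 0.9 | 13.6 | 87% |
| 1 | 15.1 | 80% |
| 1.25 | 18.8 | 61% |
| 1.5 | 22.6 | 47% |

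Over a wider span, SDs of 10, 15, 20, 25 and 30 points give 98.7%, 80.3%, 56.2%, 39.6% and 29.3% at n = 10; 80% power would need 6, 10, 16, 24 and 34 women.

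**The case against.** The 0.08 is almost certainly a misplaced decimal, and taken alone it is a one-character correction. That is accepted; the 84-point SD shows only that the printed figure cannot be meant.

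The sentence opens "Based on previous data examining chronic pharmacological intervention strategies we calculate", which suggests that the inputs came from treatment studies and that the reference to sites describes loosely where the outcome is measured. XI.1 does put treatment in the model. The site contrast is also a component of Hypothesis 1, because nitric oxide-dependent dilation is read from acetylcholine with and without L-NAME. All of this is fair, but the opening words name a data source, not a contrast, and the contrast written down is between sites. If losartan versus placebo was intended, the sentence still needs correcting.

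The numbers are conditional. Higher correlations or smaller between-visit SDs give 87% to 98% power, and a paired t-test on one contrast need not match a three-way ANOVA over ten acetylcholine concentrations. That stands, and it limits the conclusion to power not being shown.

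Finally, the last study visit is dated 08/31/2024 (VII.B.1.c), so a rewrite may come too late to affect recruitment, and nothing says a null result would be misread. Both points are true, but the restatement still governs what a null result can support.

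**Conclusion.** The concern holds. XI.2 misstates the power and attaches it to a comparison that is not the trial's question; no power, effect size or SD for losartan versus placebo appears in the documents provided.

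The size of the gap depends on SDs that the plan does not give. Reading 0.08 as 0.80 and 15% as 15 points, 10 completers could have anything from 47% to 96% power for a 15-point losartan effect at one site (between-visit SD 1.5 down to 0.75 times the between-site SD). For treatment by site the range is 51% to 98% (correlation 0 to 0.75). Ten completers are enough for a 15-point effect if the paired SD is about 15 points or less, but the plan does not show that it is. The accrual arithmetic is sound.

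**What to change.** Rewrite the XI.2 paragraph:

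- Replace the power of 0.08 with the value actually used.
- State whether 15% is absolute, relative or standardised, and whether the test is two-sided.
- From the previous data already cited, give the within-woman SD of the between-visit difference, and the correlation between sites of that difference.
- With 10 completers, report the power or the detectable difference for (a) losartan minus placebo at the acetylcholine site perfused with Ringer's alone and (b) the treatment-by-site contrast between the acetylcholine sites with and without L-NAME.
- If no between-visit SD is available, say so and show a range.

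The cost is one paragraph. Enrolment, procedures and the analysis model stay as they are. The power or detectable effect may look less favourable than the present sentence suggests. If recruitment has closed, the paragraph should be marked as written afterwards and based on the prior data, not on this trial's results.
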